#### Specific aims

1. Demonstrate the feasibility of implementing PiPT in a US Navy shore-based health care setting. We will analyze SOAP notes to assess whether the clinicians have applied aspects of the training in the treatment given to the patients and they are reflected in the notes.
2. Document and compare baseline risk factors related to pain interference in two cohorts of patients with MSD.
3. Demonstrate the effectiveness of a PiPT intervention on psychological and functional work outcomes in a comparative effectiveness trial through a relative increase in protective follow-up measures such as quality of life, self-efficacy, and satisfaction and a relative decrease in detrimental measures like pain catastrophizing, fear of movement, and distress.

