### Treatment

- After signing the consent form, the participant will complete a paper form collecting contact information for follow-up and demographic information. At this point, the participant will be assigned a participant ID number. The researcher will verify the participant's diagnostic code and therapist using AHLTA afterward.
- Before the participant's next PT appointment, the participant will complete the baseline questionnaire battery, a 139 question survey battery. The participant may complete the battery immediately on paper, or at a later date online using a link to REDCap that will be sent via encrypted email. This battery must be completed before their next appointment.
- Participants will receive PT care as prescribed and scheduled by their therapist. Participation in the study will not directly alter their care plan.
  - During Phase II, we anticipate that therapists who completed PiPT training will incorporate the training into their standard care. We will not ask therapists to give differential treatment to patients who are enrolled in the study.
- Participants will complete follow up questionnaire battery after their 4th PT appointment, 6mo and 12mo post enrollment. The first follow-up questionnaire is a 77 question survey battery. The second and third follow-up points use a 68 question battery. All follow-up questionnaires will be completed remotely via REDCap.
- We will collect de-identified SOAP notes from randomly selected participants and review them for verbiage indicating that the therapist employed principles of PiPT. We will collect up to 30 SOAP notes, pertaining to various physical therapists and throughout various stages of treatment.

We chose to conduct this study in sequential cohorts rather than conducting the two cohorts (PiPT and non-PiPT) in parallel because there are no comparable sites with similar characteristics such as type of subjects, catchment area size and availability of the health care team in the Navy.

\*We chose the 4th visit as the first follow-up point for two reasons. First, we expect to see a difference between groups on study outcomes at that point. Secondly, since according to the former head of the NMCP department of physical therapy (PI) the average number of visits at the outpatient PT clinic is 6, the 4th visit will allow us to capture complete data.

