
t e d e

a y P e ;6

st, C n 11

r F S t 31

o o V q

p ll a u

hio rie

zi w a st

n - blio

g U e n

p s

1

,

2

,

3

B

a

s

e

li

n 0

e D -

F S e 6

e u p s

a r e c

r v n al

ofe d e

my F e ;6

o , A n 12

v B t 52

e o Q V q

mll a u

e o rie

n w a st

t - blio

U e n

p s

1

,

2

,

3

B  
a  
s  
e  
li  
n 4  
e Dp  
S et  
u ps  
r ec  
D v nal  
is e de  
tr y A n 6  
e ' D t 4  
s S Vq  
s o ll a u  
o rie  
w a st  
- blio  
U en  
p s  
1

,

2

,

3

A

ff 5

e p

O Bct t  
r aiv Li  
g s e C k  
g e co e  
c li o n e  
o n mfo rt  
m e mu ; 8  
m S it n 4 0  
it u md q  
m r e e u  
e v n r e  
n v n r st  
t et io  
t y s n  
c n  
al s  
e

5

p

J B t  
o a Li  
b s C k  
s e o e  
o li n rt  
cin D fo; 8  
cin R u 1 4  
s S R n 2 4  
u u d q  
p r e u  
p v r e  
o e st  
rty io

n

s

1

-

5

B s  
a c  
s C  
e o

li P n al  
n Cfoe 7  
eL u ; 7  
S- n 1  
uMd 7  
r eq  
v ru  
e e  
y st  
io  
n  
s  
0  
-

B 3  
a s  
Ds Cc  
e e o al  
p li Cn e  
r nE fo; 7  
e eSu 2 4  
s S- n 0  
siuDd q  
o r e u  
n v r e  
e st  
y io  
n  
s  
0

B -  
a 3  
s C s  
e o al  
A li Gn e  
n nA fo; 7  
xieDu ; 7 6  
e S- n  
tyu 7 d q  
r e e  
v r st  
e io  
y n  
s

B  
a  
s  
e  
li  
n  
e  
M S  
e u  
n r C  
t v h o Y  
al e h n Y  
H r fo e n  
e e e s n  
al' e u / /  
t F n a  
t o d N  
h ll e o  
C o m r  
a w  
r -  
e u  
p  
1  
,

,  
3  
B  
J a  
o s C  
b e Sio 1  
s l i n n -  
a n g l f o 5 7  
t i e e u s 9  
s f S i t n c  
a u e d a l  
c t r m e e  
i o v r  
n e

y  
B  
a  
W s C  
o e Sio 1  
r l i n n -  
k n g l f o 5 n  
s t e e u s /  
r S i t n c a  
e u e d a l  
s r m e e  
s v r  
e  
y

F  
u l  
B I  
a D  
s u  
e t  
l i y  
n ;  
e Li  
S m  
u it  
Dr e  
u v Sio d  
t y e n n D  
S y g l f o t n  
t , e u y /  
a F i t n a  
t o e d ;  
u l l m e M  
s o r e  
w d  
- B  
u o  
p a  
1 r  
, ;  
2 O  
, t  
3 h  
e  
r

P  
e  
rc D  
e i B e F  
v a p r  
e s e e  
d e S i n e  
b l i n d R  
a n g l e R  
r r e e n e

ieSItt s 1  
rsue V p 1  
r ma o  
t v rin  
o e as  
c y ble  
a e  
r  
e

Follow-up Questionnaire Batteries

- Post 4th treatment session- 77 items long, including one open field question
- 6 and 12mo – 68 items (excludes MRPS scale and outcome expectation)

C  
o V  
II a R C  
A e rie i  
R c ass i  
T ti b p t  
I O l o a  
A O l o t  
B L en i  
P T s o  
L o y e n  
E i p s n  
n e  

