## 11.6 Data Analysis Plan: Complete description: Background, Objectives, Design, Step by Step how the project is going to be done, Data analysis plan:

In order to assess for significant differences between two cohorts of patients, bivariate comparisons will first be conducted using a Chi-squared (Fisher exact) test to compare proportions of categorical (dichotomous outcomes) and an unpaired t-test for mean changes of continuous outcomes (i.e. Pain Disability Index scale, self-efficacy, positive outcome expectation, catastrophizing, fear avoidance beliefs and distress).

Alternatively, Wilcoxon nonparametric counterpart will be used for continuous variables where there is deviation from normality. These univariate analyses will be followed by multivariable regression methods for an adjustment of all other potential confounding variables. We will also use longitudinal logistic models (i.e., mixed-effects regression models with a random subject effect and GEE with exchangeable and independent correlations) to analyze the changes of the outcome at baseline at all follow-up times (baseline, post-treatment, at 6 months, and 1 year). Psychological outcomes will be analyzed at baseline and at post-treatment (approximately 4 weeks of enrollment). The models will be specified with random intercepts and slopes such that a linear trajectory representing outcomes will be compared between two arms. For example, longitudinal changes in all available continuous psychological outcomes over time of follow-up will be displayed using locally weighted smoothing scatter (lowess) plots, identifying nonparametric mean trajectories over time. Mean trajectories then will be modeled with mixed-effects linear regression models, and if necessary using segment-linear models to approximate non-linear mean trajectories for ease of interpretation. Group (arm)-specific (as well as individual-level) intercepts and slopes over the period of follow-up will be included as random effects, while other covariates such as other clinical or demographic confounders will be modeled as fixed effects. An interaction term will be also assessed to test group differences in outcomes over time. Residual-based diagnostics will be used to evaluate validity of model assumptions. Two sided p-values <0.05 will be considered to be statistically significant. All statistical procedures will be performed using R statistical package ([www.R-project.org](http://www.R-project.org)).

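### Six continuous outcomes are each tested at two-sided 0.05 with no primary outcome, time or multiplicity control: about 16-26% chance of a false significant difference at one visit (8-14% in PiPT's favour, nominal 2.5%)

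*Combined protocol and SAP*

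**What the plan says.** Section 11.6 compares the cohorts by unpaired t-test on mean change in six continuous outcomes: "i.e. Pain Disability Index scale, self-efficacy, positive outcome expectation, catastrophizing, fear avoidance beliefs and distress". A Wilcoxon test is the fallback. Multivariable regression and longitudinal models (mixed-effects and GEE) follow, with a group-by-time interaction. The only criterion for significance is "Two sided p-values <0.05 will be considered to be statistically significant".

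On timing, Section 11.6 says two things. The longitudinal models cover outcomes "at all follow-up times (baseline, post-treatment, at 6 months, and 1 year"). The next sentence reads: "Psychological outcomes will be analyzed at baseline and at post-treatment (approximately 4 weeks of enrollment").

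The follow-up battery in Section 10.2 collects five of the six outcomes at all three follow-ups. Outcome expectation is collected only at the first, because the 6- and 12-month battery "excludes MRPS scale and outcome expectation".

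Aim 3 in Section 9.3 is to demonstrate effectiveness through "a relative increase in protective follow-up measures such as quality of life, self-efficacy, and satisfaction and a relative decrease in detrimental measures". It does not say how many measures must improve, or which. The note on the 4th visit in Section 10.1 says of that time point that "we expect to see a difference between groups on study outcomes at that point".

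The power text in Section 11.6 uses two-sided 0.05, takes PDI as an example and states that power is the same for each domain outcome. Only the sub-analysis of participants who endorse the mental care questions is labelled exploratory.

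**The concern.** A 5% threshold on each of six tests does not hold the error at 5% for the set. With no primary outcome and no success criterion, nothing in the plan prevents one nominally significant result from being presented as the demonstration that Aim 3 calls for. The power calculation treats each outcome as though it were the only one tested, so the plan takes full power for each outcome and pays nothing for testing several.

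At stake is how far a positive report on Aim 3 could be trusted. A reader could not tell whether a single significant scale was the intended test or the best of several.

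**Working it through.** **Inputs from the documents.** Two-sided 0.05 per test, which is 0.025 in each direction (11.6). Six continuous outcomes (11.6). Three post-baseline times (10.1, 11.6). Outcome expectation at the first follow-up only (10.2). Standardized difference 0.3, 200 completers per cohort, 30% loss (11.5; Table 2 in 11.6). The documents give no correlations between outcomes or visits, so those below are assumptions.

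**Step 1. The plan's own figure.** 286 × 0.70 = 200 completers per cohort. The noncentrality parameter is 0.3 × √(200/2) = 3.0 on 398 degrees of freedom, and the noncentral t gives 84.9% power at two-sided 0.05. Table 2 states 84.9%, so it reproduces, as a single test at an undivided 0.05.

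**Step 2. Six outcomes at one visit.** If the tests are independent:
- either direction: 1 − 0.95^6 = 26.5%
- favouring PiPT: 1 − 0.975^6 = 14.1%

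For correlated tests I used 200,000 multivariate normal draws with exchangeable correlation. All outcomes were scored so that higher favours PiPT, and the critical value was 1.96.

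| Between-outcome correlation | Either direction | Favouring PiPT |
|---|---|---|
| 0 | 26.5% | 14.1% |
| 0.3 | 24.2% | 12.3% |
| 0.5 | 20.5% | 10.2% |
| 0.7 | 16.4% | 8.2% |

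The comparators are 5% in either direction and 2.5% in PiPT's favour.

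**Step 3. Over follow-up.** The count depends on the reading of 11.6.
- Separate tests at each visit: 5 outcomes × 3 visits + 1 = 16 at most.
- Psychological outcomes after treatment only, with PDI (not counted as psychological) at three visits: 3 + 5 = 8.

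| Correlation between outcomes, between visits | 16 tests: either / favouring PiPT | 8 tests: either / favouring PiPT |
|---|---|---|
| 0.3, 0.5 | 47.9% / 25.3% | 30.0% / 15.3% |
| 0.5, 0.5 | 42.5% / 21.8% | 26.9% / 13.5% |
| 0.7, 0.7 | 30.9% / 15.5% | 20.9% / 10.5% |

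Under full independence the limits are 1 − 0.95^16 = 56.0% and 1 − 0.975^16 = 33.3% for 16 tests, and 33.7% and 18.3% for 8.

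**Step 4. Power under possible remedies** (t-test, d = 0.3, 200 per cohort).
- One named primary at 0.05: 84.9%.
- Strictest Holm step with five secondary outcomes, 0.05/5 = 0.01: 66.0%.
- Strictest Holm step with eight (those five, quality of life and the two satisfaction measures), 0.05/8 = 0.00625: 59.9%.
- For comparison, Bonferroni over all six with no primary, 0.05/6 = 0.0083: 63.6%. Restoring 80% would need 270 completers per cohort, or 270/0.70 = 386 enrolled.

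**The case against.** The strongest case against the point has five parts.

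- **The study type.** Section 9.4 describes an observational hybrid type 3 study, and Aim 1 is feasibility. Strict error control is less pressing here than in a confirmatory randomised trial. This lowers the urgency, but Aim 3 still sets out to demonstrate effectiveness, and its outcomes carry no exploratory label.
- **Direction.** A reader might take 16-26% as the chance of wrongly claiming that PiPT works. The documents do not support that. Aim 3 is directional, and the either-direction rate includes differences against PiPT. The rate for a false result in PiPT's favour is about half as large.
- **The success rule.** A reader might infer that improvement in any one measure meets Aim 3. The text does not say so: it names protective and detrimental measures in the plural, joined together. The gap is an absent success criterion, not a stated lenient one.
- **The number of tests.** A reader might multiply six outcomes by three visits to get 18. Outcome expectation is not collected at 6 and 12 months, so 16 is the ceiling. The plan does not say that the t-test is repeated at each visit, and one sentence confines psychological outcomes to baseline and post-treatment. A longitudinal model could also yield one test per outcome. That would be six correlated tests, for which the one-visit figures are the nearer guide.
- **The choice of primary.** PDI is only an example in the power text, and Section 9.2 sets out to test long-term as well as short-term effectiveness. Naming PDI at the 4th visit is therefore a choice for the investigators, and it ranks the short-term result above the long-term one.

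These points change the size and description of the problem. None brings the error back to its nominal level.

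**Conclusion.** The point holds. Six outcomes are each judged at two-sided 0.05 with no primary outcome, no primary time, no multiplicity control and no success criterion for Aim 3.

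At one visit, the error in PiPT's favour is roughly three to six times the nominal 2.5% (8.2/2.5 = 3.3; 14.1/2.5 = 5.6). The all-visit figures are less certain, because they rest on how two sentences of Section 11.6 are read as well as on assumed correlations (0.3-0.7 between outcomes, 0.5-0.7 between visits). On either reading of the analysis times the error stays above nominal.

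All figures suppose no true difference and no confounding between the sequential cohorts. Six is also a low count. Aim 3 adds quality of life and satisfaction, and Section 11.6 adds dichotomised outcomes, adjusted and unadjusted analyses, two longitudinal approaches and an interaction test, none designated as decisive.

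**What to change.** In Section 11.6:

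1. Name one primary outcome, time and analysis for Aim 3 at two-sided 0.05. Change in PDI from baseline to the follow-up after the 4th visit, estimated from the confounder-adjusted model, fits the plan's own power example and the time at which Section 10.1 expects a difference. The model and its covariates should be fixed before outcome data are examined.
2. Test the other Aim 3 outcomes at that visit with a Holm adjustment, including quality of life and satisfaction. The satisfaction measures have no baseline value in Section 10.2, so they would be compared as levels.
3. Report the 6- and 12-month results as secondary estimates with confidence intervals.
4. Reconcile the two sentences on analysis times, and state what result would count as demonstrating effectiveness.

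The cost is SAP wording and an explicit decision to rank the short-term result first. No participants are added. A t-test on the primary keeps 84.9% power at d = 0.3 with 200 per arm. Power of the adjusted model is not given in the documents and would depend on the covariates. The strictest Holm step has about 66% power with five secondary outcomes, and about 60% once quality of life and satisfaction are included.

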### 11.4 If you are recruiting by study arm, please identify the arms of the study and how many subjects will be enrolled in each arm

300 in the pre-training arm (control arm)  
300 in the post-training arm (intervention arm)

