### 11.5 Please provide a justification for your sample size

In order to achieve a statistical power of greater than 80% at an effect size of 0.3, we require a minimum of 200 participants to complete all follow-up in each cohort of the study, as detailed in the power analysis in Section 11.6. In order to account for a roughly 30% rate of attrition, we are requesting a sample size of 300 participants per arm, for a total of 600. Based on previous longitudinal studies by team members [name], [name], and [name], we believe that this is a conservative estimate considering the duration of each participant's involvement.

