In order to determine the association of treatment effects among the subjects who endorse the mental care questions, we will further perform the sub-analysis using the regression analysis similarly stated as above. All covariates and their source are shown in the tables of variables found in Section 10.2. This analytic approach will be hypotheses generating and will be largely exploratory as the study may not be powered to detect significant effects. Therefore, we have not proposed any formal power calculation for the sub-analysis.

Assuming normality, we calculated the statistical power for various detectable effect sizes and sample sizes in a two-sided hypothesis test with a significance level of 0.05, where the ratio of sample size of 1:1 is assumed between cases (intervention arm) vs. controls. When outcomes are proportions, we calculated power based on rate differences. Table 2 shows that our sample size will have adequate power to detect listed effect sizes. For example, we will achieve 95.4% power to detect a difference of rate of 0.3 (i.e., achieving minimal clinically important difference of 80% in receiving therapy by PT staff "after training" group vs. 50% in receiving therapy by PT staff before training) between two arms of a size of 100 (117) for each with 30 (40) % of missingness. For continuous outcomes, the same size of n=100 (117) for each will have a 83.6% power to detect standardized mean difference of 0.5, which corresponds that the reduction in PDI (Pain Disability Index) score from baseline to follow-up would be 50% greater in the training group as compared to that before training. Note that for each domain outcome, the power is the same for each effect size since they are standardized, but the mean change corresponding to a given effect size differs.

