**Table 2. Sample size and power**

Cohort size N (Total sample)	Loss to follow-up or noncompliance	Unpaired t- test	Fisher exact test			
			Effect size 	Power (%)	Effect size 	Power (%)
117 (234)	40%				0.30 (p1=0.8, p2=0.50)	95.4
100 (200)	30%	0.5	83.6			
167 (334)	40%				0.25 (p1=0.8, p2=0.55)	95.8
143 (286)	30%	0.5	94			
250 (500)	40%				0.20 (p1=0.8, p2=0.6)	96
215 (430)	30%	0.4	93.2			
334 (668)	40%				0.15 (p1=0.8, p2=0.65)	96
286 (572)	30%	0.3	84.9			

1 standardized mean difference of 2 groups  
2 absolute proportion difference of 2 groups with proportions ( $p_1 = P(\text{above MID in pre-training cohort})$ ,  $p_2 = P(\text{above MID in post-training cohort})$ )

**Missing data:** We will make every effort to prevent and avoid missing data. Even with the most robust processes, however, some missing data is inevitable. We will assess the mechanism of missing data by comparing patients with and without missing values on baseline and other complete information, to detect any patterns in demographics or other characteristics associated with missing data. First, the various missingness assumptions (missing completely at random: MCAR, missing at random: MAR or missing not at random: MNAR) will be tested by comparing subjects with missing and non-missing data. In order to incorporate uncertainty in handling missing data, we will perform a multiple imputation, which begins with a prediction of the missing data using the existing data from other variables. The missing values will then be replaced with the predicted values, and a full data set called the imputed data set will be created. This process iterates the repeatability and makes multiple imputed data sets. Each multiple imputed data set produced will be then analyzed using the standard statistical analysis procedures for complete data, and give multiple analysis results. Subsequently, by combining these analysis results, a single overall analysis result will be produced.

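### Table 2's bolded responder row prints 96% power, which neither its own 200 completers per arm (90.7%) nor the enrolled 300 per arm (92.1% at 30% loss, 87.2% at 40%) delivers, and footnote 2 reverses the cohorts.

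*Combined protocol and SAP*

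**What the plan says.** Section 11.6 computes power "in a two-sided hypothesis test with a significance level of 0.05", with 1:1 allocation, and concludes that "Table 2 shows that our sample size will have adequate power to detect listed effect sizes". Table 2 uses the unpaired t-test for continuous outcomes and the Fisher exact test for proportions.

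Two lines of Table 2 are bolded:

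- 334 per arm (668), 40% loss, responder effect "0.15 (p1=0.8, p2=0.65"), power 96%.
- 286 per arm (572), 30% loss, standardized mean difference 0.3, power 84.9%.

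Sections 11.2 and 11.3 give a total of 600. Section 11.4 gives 300 in the control arm and "300 in the post-training arm (intervention arm"). Section 11.5 aims for more than 80% power at an effect size of 0.3, says that "we require a minimum of 200 participants to complete all follow-up in each cohort of the study", and reaches 300 per arm by allowing for roughly 30% attrition.

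On the rates, the worked example in section 11.6 puts 80% in the group treated after training and 50% in the group treated before it. Footnote 2 of Table 2 defines p1, which is 0.8 in every row, as the probability of being "above MID in pre-training cohort", and p2 as the post-training probability.

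**The concern.** The text presents Table 2 as the power of the study as sized, yet the bolded responder row carries an enrolment 68 patients above the plan (668 − 600) and a loss rate that section 11.5 does not use. The printed 96% also looks too high: it equals the cell above it, although the difference to be detected falls from 0.20 to 0.15 while completers per arm rise only from 150 to 200.

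Table 2 is the plan's only stated support for power on responder outcomes, so a wrong figure there will be carried into any report that cites it. The footnote adds a second problem. Read literally, it has every row powering a fall in response after training, the reverse of the study's hypothesis.

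**Working it through.** **Inputs.** Two-sided alpha 0.05, 1:1 allocation, Fisher exact test and unpaired t-test (section 11.6 and Table 2). Rates, effect sizes, cohort sizes and loss rates are from Table 2. Enrolment of 300 per arm, about 30% attrition and the 200-completer minimum are from sections 11.4 and 11.5.

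**Completers per arm** = N × (1 − loss).

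- Bolded rows: 334 × 0.6 = 200.4 and 286 × 0.7 = 200.2, so 200 in both.
- Enrolled study: 300 × 0.7 = 210 and 300 × 0.6 = 180.
- The 200 minimum is met while loss is at most 1 − 200/300 = 33.3%.

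**Formulas.**

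- Fisher: power = Σ Bin(x; n, p1) × Bin(y; n, p2), summed over all (x, y) whose two-sided Fisher p-value is at most 0.05 (full enumeration).
- t-test: noncentral t with 2n − 2 degrees of freedom and noncentrality d√(n/2).

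**Reproducing Table 2.**

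| Row | Completers per arm | Effect | Printed | Recomputed |
|---|---|---|---|---|
| 117, 40% | 70 | 0.80 vs 0.50 | 95.4 | 95.4 |
| 167, 40% | 100 | 0.80 vs 0.55 | 95.8 | 95.8 |
| 250, 40% | 150 | 0.80 vs 0.60 | 96 | 96.0 |
| 334, 40% | 200 | 0.80 vs 0.65 | 96 | **90.7** |
| 100, 30% | 70 | d = 0.5 | 83.6 | 83.6 |
| 143, 30% | 100 | d = 0.5 | 94 | 94.0 |
| 215, 30% | 150 | d = 0.4 | 93.2 | 93.2 |
| 286, 30% | 200 | d = 0.3 | 84.9 | 84.9 |

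Seven of eight cells reproduce. The bolded responder cell does not.

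**Could another method give 96% at n = 200?** Two-sided alternatives give 92.2% (pooled z), 92.6% (unpooled z), 90.4% (continuity-corrected z) and 92.3% (arcsine). The pooled z can be checked by hand: mean rate 0.725; (0.15 − 1.96 × √(2 × 0.725 × 0.275/200)) / √((0.16 + 0.2275)/200) = (0.15 − 0.0875)/0.0440 = 1.42, and Φ(1.42) = 92.2%. A one-sided pooled z gives 95.9% and one-sided Fisher 95.0%. However, the plan states a two-sided test, and one-sided Fisher would turn the three cells that match into 97.6, 98.0 and 98.1. A two-sided Fisher power that rounds to 96% (95.5%) needs about 246 completers per arm, more than 334 × 0.6 = 200 or 300 × 0.7 = 210.

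**Power at the enrolled size.**

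| Enrolled per arm | Loss | Completers | 0.80 vs 0.65 (Fisher) | d = 0.3 (t-test; noncentrality) |
|---|---|---|---|---|
| 300 | 30% (plan's assumption) | 210 | 92.1% | 86.6% (0.3√105 = 3.07) |
| 300 | 40% (sensitivity) | 180 | 87.2% | 81.0% (0.3√90 = 2.85) |

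**Splitting the gap.** At 40% loss it is 96 − 87.2 = 8.8 points: 96 − 90.7 = 5.3 from the cell being wrong at its own size, and 90.7 − 87.2 = 3.5 from enrolling 300 instead of 334. At 30% loss it is 96 − 92.1 = 3.9 points, none of it due to enrolment, since 210 completers exceed the row's 200.

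**Footnote 2.** Text: 80% after training, 50% before. Footnote: p1 = 0.8 before, p2 = 0.50 to 0.65 after. A gain starting from 0.8 could not be 0.25 or 0.30, because 0.8 + 0.25 = 1.05 and 0.8 + 0.30 = 1.10. The text's assignment is the coherent one. A two-sided test with equal arms has the same power whichever cohort is called p1.

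**The case against.** The strongest reply is that the 334 (668) line is not a claim about 600 patients. Table 2 pairs enrolments that give equal completers: 117 at 40% loss with 100 at 30%, up to 334 at 40% with 286 at 30%. The worked example in section 11.6 says as much, quoting one power for 100 (117) per arm with 30 (40)% missing. On that reading the bolded responder power rests on 200 completers, which 286 per arm at 30% loss also supplies, within 600. Section 11.5 assumes about 30% attrition, and 300 per arm then gives 210 completers, above its minimum.

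This is right, and it limits the point. A reader might infer that under-enrolment costs the study about 9 points of responder power, or that the plan promises 96% power for 600 patients at 40% loss. The documents support neither. The 40% line prints 668, section 11.5 does not assume 40% loss, and most of the 8.8 points is the erroneous cell, so raising enrolment to 334 would give only 90.7%.

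The reply does not rescue the 96%. Whichever member of the pair is used, 200 completers give 90.7%, and the table still has no row for the size actually enrolled.

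**Conclusion.** The printed 96% is wrong at the row's own size and is not reached by the planned study at either tabulated loss rate. The correct values for 0.80 vs 0.65 are 90.7% at 200 completers per arm, 92.1% at the plan's 30% loss and 87.2% at 40% loss. The last is a sensitivity case with 180 completers, below the minimum in section 11.5. The footnote contradicts the text on which cohort has the 80% rate.

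It would be tempting to conclude that the study is underpowered. It is not, on the plan's own terms: every effect listed in Table 2 keeps more than 80% power at 300 per arm, even at 40% loss (the lowest is 81.0%, for d = 0.3), so the adequacy claim stands. Power below 80% appears only for a contrast that the table does not list. For example, 50% vs 65% at 180 completers gives 79.2%, and 86.2% at 210. Nor does the footnote mean that the calculation targets harm; it is a labelling slip with no effect on power.

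These results assume two-sided Fisher testing at 0.05, equal arms, loss at the same rate in both cohorts, and the responder rates in Table 2. The repeated 96 may be a carry-over from the row above, but the documents cannot confirm that.

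**What to change.** 1. In Table 2, change the power for 0.80 vs 0.65 at 200 completers per arm from 96 to 90.7.
2. Add rows for the enrolled 300 (600), or substitute them for the bolded ones: 30% loss, 210 completers, 92.1% (0.80 vs 0.65) and 86.6% (d = 0.3); 40% loss, 180 completers, 87.2% and 81.0%. Mark the 40% row as a sensitivity case below the 200-completer minimum.
3. In footnote 2, swap the labels so that p1 = 0.8 is the post-training cohort and p2 the pre-training cohort, as in the text of section 11.6.

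The cost is a few table figures and one footnote. No patients are added and no analysis changes. The stated responder power becomes slightly less favourable and stays above 80%.
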